10.4.3 Analysis of the Secondary and Exploratory Endpoint(s)

For non-primary comparisons, an α level of 0.05 will be used for significance. We will test the main effects of treatment condition on percent initial weight change at skin carotenoid levels, general health and weight-related quality of life as well as exploratory endpoints using linear mixed models and similar methods as described above. Analyses will use intention-to-treat analyses and will be conducted with and without adjustment for baseline differences in characteristics. We plan to assess for differential effects of the interventions based on sex/gender and race/ethnicity. Separate analyses will be performed for men and women and based on self-identified race/ethnicity, although these will be considered exploratory as there is no strong reason to hypothesize a difference in efficacy based on these characteristics.

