3 STUDY OBJECTIVES AND ENDPOINTS

OBJECTIVES	ENDPOINTS
Primary	
Test the hypothesis that BWL+VOUCHER and BWL+HOME will result in greater weight loss (percent of initial weight) at 24 weeks than BWL-Alone.	P initial weight loss at week 24
Secondary	
Test the hypothesis that BWL+HOME will result in greater weight loss (percent of initial weight) at 24 weeks than BWL+VOUCHER.	P initial weight loss at week 24
Test the hypothesis that BWL+VOUCHER and BWL+HOME, relative to BWL-Alone, produces greater improvements from baseline to week 24 in: General health-related quality of life (QOL)	Change from baseline to week 24 in general health-related quality of life as assessed with the Short Form (SF)-36
Weight-related QOL	Change from baseline to week 24 in weight-related quality of life as assessed with the Impact of Weight on Quality of Life(IWQOL)-Lite
Dietary quality as assessed by skin carotenoid levels (a fruit and vegetable biomarker)	Change from baseline to week 24 in skin carotenoid levels
Healthy Eating Index (HEI) scores	Change from baseline to week 24 in Healthy Eating Index scores as measured with the ASA24
Test the hypothesis that BWL+HOME, compared to BWL+VOUCHER, produces greater improvements from baseline to week 24 in: General health-related QOL	Change from baseline to week 24 in general health-related quality of life as assessed with the Short Form (SF)-36

OBJECTIVES	ENDPOINTS
Weight-related QOL	Change from baseline to week 24 in weight-related quality of life as assessed with the Impact of Weight on Quality of Life (IWQOL)-Lite
Skin carotenoid levels	Change from baseline to week 24 in skin carotenoid levels
HEI scores	Change from baseline to week 24 in Healthy Eating Index scores as measured with the ASA24
Tertiary	
Test the hypothesis that BWL+VOUCHER and BWL+HOME, relative to BWL-Alone, produces greater improvements from baseline to week 24 in: Food security scores	Change from baseline to week 24 in food security scores as assessed by the USDA Food Security Measure
Binge eating and eating disorder psychopathology	Change from baseline to week 24 in binge eating and global eating disorder psychopathology as measured by the Eating Disorder Examination Questionnaire
Depressive symptoms	Change from baseline to week 24 in depressive symptoms as measured by the Patient Health Questionnaire 8
Weight-loss-related behaviors	Change from baseline to week 24 in weight-loss-related behaviors as measured by the Eating Behavior Inventory

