4 STUDY PLAN

4.1 Study Design

The single-site, open-label, phase 2, three-arm RCT will enroll 105 participants recruited from the community who will be randomly assigned to one of three groups, all of which will receive BWL. Groups include: BWL-Alone (including standard-of-care referral and connection with community food resources); BWL combined with food vouchers (BWL+VOUCHER); and BWL combined with home-delivered, medically tailored groceries (BWL+HOME). Each intervention will be provided for 24 weeks. We hypothesize that participants in BWL+VOUCHER and BWL+HOME will achieve greater improvements in weight, self-reported and objective markers of dietary quality, and health-related quality of life relative to BWL-Alone. Further, we predict that participants in BWL+HOME will experience greater improvements in weight, dietary quality, and quality of life than BWL+VOUCHER. Assessments will occur at weeks 0, 12, and 24.

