5.5 Measures to Minimize Bias: Randomization and Blinding

A permuted block randomization method will be used to assign participants to one of the three intervention groups in a 1:1:1 ratio. Once eligibility is confirmed, intervention assignment will be made by a pre-programmed randomization scheme. Block sizes will be varied to minimize potential bias, and randomization will be stratified by baseline SNAP/WIC receipt (vs no receipt). All participants who are randomized will be entered into the study database and analyzed according to Consolidated Standards of Reporting Trials guidelines for multi-arm parallel-group randomized trials.¹¹¹ This is an open-labelled randomized trial.

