9 STUDY ASSESSMENTS

9.1 Efficacy Assessments

Research staff will conduct assessments at our Center at weeks 0 (baseline), 12 and 24. All measures will be administered at all timepoints. Assessment staff will receive training in adherence to the data collection protocol. Questionnaires will be completed on REDCap, a secure, web-based program (if requested, participants can completed questionnaires on paper). To provide compensation for time and travel, participants will be paid \$40 per assessment. We will provide participants with ClinCards, which are similar to debit cards, that we have used for other studies. This form of payment allows us to load money remotely, enabling us to compensate participants soon after they complete study tasks.

Demographic and neighborhood data. Standard questionnaires will be administered to collect data on demographics at week 0 including age, biological sex, gender, race/ethnicity, income, street address, zip code, receipt of SNAP and/or WIC, household size, disabilities, marital status, and highest education level. We will recollect these data at weeks 12 and 24 to account for changes in status. We will also collect descriptive data at each timepoint on neighborhood food and physical activity environment including the Perceived Nutrition Environment Measures Survey¹³³ and Neighborhood Environment Walkability scale.¹³⁴

Weight and height. Weight will be measured in light clothes and no shoes, after an 8-hour fast, using a standardized scale calibrated monthly and accurate to 0.1 kg. Weight will be measured in duplicate. Height will be assessed in duplicate with a wall-mounted stadiometer at baseline.

Quality of life. General health-related quality of life (HRQOL) will be assessed by the Short Form (SF)-36, which contains 36 items that measure subjective health status.¹¹⁹ The scale forms two summary measures—a physical and mental component summary. Scores are transformed using a 0 to 100 scale, with higher scores indicating better HRQOL. Weight-related quality of life will be measured with the 31-item IWQOL-Lite scale.¹²⁰ The measure generates a total score ranging from 0 (worst) to 100 (best).

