10.4.2 Analysis of the Primary Efficacy Endpoint(s)

The two primary outcomes are to test the hypotheses that each of the BWL+VOUCHER and BWL+HOME interventions will result in better weight loss at week 24 compared to BWL-Alone. The primary analysis is an intention-to-treat, between-group comparison of the mean change from baseline (randomization) to week 24 using a linear mixed model. Specifically, we will regress the mean change from baseline on the treatment indicator and baseline weight loss. Significance will be determined using an α cutoff of 0.05. The primary analysis will be an intent-to-treat analysis. The model will include each participant as a random intercept to adjust for within-patient correlation of the repeated measures, fixed predictors of study arm indicators, time indicators, and time by study arm interactions. In addition, sensitivity analyses will be conducted adjusting the model by including baseline variables that either had between-group differences at baseline or that were associated with the likelihood of missing outcomes at a 0.20 significance level.

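### Section 10.4.3 does not commit to each secondary endpoint's own baseline value as a covariate, and leaving it out would cost precision in the Aim 3 contrasts

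*Combined protocol and SAP*

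**What the plan says.** Section 3 defines the Aim 3 endpoints as changes, for example "Change from baseline to week 24 in skin carotenoid levels". Section 9.1 ensures that the week 0 value exists for each of them: "All measures will be administered at all timepoints".

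Section 10.4.3 gives no covariate list for these endpoints. It refers to "linear mixed models and similar methods as described above" and adds that analyses "will be conducted with and without adjustment for baseline differences in characteristics". It does not say which of the two versions is the main one. Section 10.4.1 explains how such variables are found: key baseline variables that turn out to differ by arm are considered as covariates.

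The method referred to is the weight model in 10.4.2, which is described in two ways:

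- First description: "we will regress the mean change from baseline on the treatment indicator and baseline weight loss". This has a baseline term, but no weight loss from baseline exists at baseline, so the variable is undefined.
- Second description: a random intercept per participant with arm, time and arm-by-time terms. No baseline term is listed.

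Section 10.4.2 also plans sensitivity models that add baseline variables which differ between arms, or which predict missing outcomes at the 0.20 level.

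**The concern.** Change in a questionnaire score, a diet index or a carotenoid reading usually depends on where the participant started. A model without that starting value leaves the variation in the error term, and any chance imbalance at baseline passes into the estimated contrast. A statistician who follows the second description in 10.4.2 literally gets this result. With complete data, a random-intercept model that has week 0 as a response row and free arm means returns the plain difference in mean change.

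Adjusting only when the arms are seen to differ is a weaker rule than adjusting always, because it leaves the model to be chosen after the data are seen. Precision matters here because section 10.2 gives the trial's purpose as supplying effect sizes for planning a larger trial.

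**Working it through.** **Inputs from the documents.** Section 4.1: "three-arm RCT will enroll 105 participants". Section 5.5: "assign participants to one of the three intervention groups in a 1:1:1 ratio". So 105/3 = 35 per arm, as the synopsis states. Section 10.4.3: "For non-primary comparisons, an α level of 0.05 will be used for significance"; sidedness is not stated, and two-sided is assumed. The plan gives no SD, correlation or power for any Aim 3 endpoint, so it has no figure of its own to reproduce.

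**Assumptions.** Baseline and week-24 SDs are equal (set to 1), their correlation is r, and 35 participants per arm are complete.

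**Formulas, per participant.**

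- Change score: variance = 2(1-r).
- Adjusted for own baseline: variance = 1-r².
- Ratio, adjusted to change score: (1-r²)/[2(1-r)] = (1+r)/2, so the share given up is (1-r)/2.
- Detectable difference at 80% power (normal approximation): 2.8016 × √(2 × variance/35).

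| r | Change-score variance | Adjusted variance | Share given up | SE reduction from adjusting | Detectable difference in SD, change → adjusted | Power for an assumed 0.5 SD difference, change → adjusted |
|---|---|---|---|---|---|---|
| 0.3 | 1.40 | 0.91 | 35% | 19% | 0.79 → 0.64 | 42% → 59% |
| 0.5 | 1.00 | 0.75 | 25% | 13% | 0.67 → 0.58 | 55% → 68% |
| 0.7 | 0.60 | 0.51 | 15% | 8% | 0.52 → 0.48 | 77% → 83% |
| 0.9 | 0.20 | 0.19 | 5% | 3% | 0.30 → 0.29 | above 99% for both |

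**Check by simulation.** Three arms of 35, with 20,000 runs per value of r, gave reductions of 33.9%, 23.8% and 14.4% at r = 0.3, 0.5 and 0.7. The extra degree of freedom therefore costs about one percentage point.

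**Sensitivity to the SD ratio.** With k = week-24 SD divided by baseline SD, the share is (1-rk)²/(1+k²-2rk). For r from 0.7 to 0.3:

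- k = 0.8: 37% to 50%
- k = 1: 15% to 35%
- k = 1.25: 2% to 22%

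**Sensitivity to the estimand.** Section 10.4.3 speaks of main effects of treatment. If that means the average over weeks 12 and 24 with a common correlation, the variances are 1.5(1-r) and (1-r)(1+2r)/2. The share is then 2(1-r)/3, which is 47%, 33% and 20% at r = 0.3, 0.5 and 0.7.

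**Chance imbalance.** One standard error of the baseline difference is √(2/35) = 0.24 SD. Given such an imbalance, the change-score contrast shifts by (1-r) × 0.24, which is 0.12 SD at r = 0.5.

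**The case against.** A reader might infer that the plan analyses these endpoints without their own baseline. The documents do not say that. The first description in 10.4.2 has a baseline term, and the ordinary way to carry a similar method from weight to carotenoids is to replace that term with baseline carotenoids. On that reading nothing is lost. Nor is anything lost if week 0 is a response row with arm means constrained equal. The text neither states nor excludes such a constraint. This part of the objection stands: the defect is a missing commitment, not a demonstrated wrong choice.

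A reader might also infer that observed imbalance is the only route by which a baseline variable can enter. It is not. The missingness-linked covariates in 10.4.2 are a second route, and it does not depend on arm differences. An endpoint whose baseline visibly differed by arm could also enter under 10.4.1 and 10.4.3, so the imbalance harm is partly covered. But neither route guarantees the own baseline, and both are settled after the data are seen.

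Third, 15% to 35% could be read as a property of this trial. It is not. It holds for r between 0.7 and 0.3 with equal SDs, and none of those values is in the documents.

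Lastly, the study is called exploratory and sets no power target, so the power and detectable-difference columns illustrate scale and test no claim in the plan. The exploratory aim does not remove the point, because precise effect estimates are what section 10.2 asks of the trial.

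**Conclusion.** The point holds as a gap in pre-specification. Section 10.4.3 does not commit to each endpoint's own baseline value. The model it borrows has either an undefined baseline term or none, and the adjustment it states itself depends on observed arm differences.

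If the own baseline is left out, the loss is (1-r)/2 of the contrast's variance under equal SDs: 35%, 25%, 15% and 5% at assumed r of 0.3, 0.5, 0.7 and 0.9. It is larger or smaller when the SDs differ. If the sponsor already intends an own-baseline term, the loss is zero and the fix only records the intention.

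This is about precision and about fixing the model in advance. The randomised change-score comparison remains valid on average.

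**What to change.** In 10.4.3, state that each continuous secondary and exploratory endpoint is analysed with its own baseline value as a covariate, regardless of observed imbalance, with weeks 12 and 24 as the response rows. Week 0 as a response with arm means constrained equal is an acceptable equivalent. Name this as the main analysis and keep the version without baseline adjustment as supportive.

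Add HEI by name: it is an Aim 3 endpoint in sections 3 and 10.1, but 10.4.3 does not list it. In 10.4.2, replace the baseline weight-loss term with a defined variable, so that the cross-reference from 10.4.3 points to a clear model.

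The cost is a sentence or two of text and one degree of freedom per model. The baseline values are already collected at week 0.

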10.2 Sample Size Determination

This is an exploratory study. The sample size should be sufficient to provide us with effect size estimates for a larger randomized controlled trial.

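### Differential effects by sex/gender and race/ethnicity are to be assessed by separate subgroup analyses alone, with no planned estimate, interval or test of the difference between subgroup effects

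*Combined protocol and SAP*

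**What the plan says.** Section 10.4.3 states the aim: "We plan to assess for differential effects of the interventions based on sex/gender and race/ethnicity". The next sentence gives the method: "Separate analyses will be performed for men and women and based on self-identified race/ethnicity", with the qualification that "these will be considered exploratory as there is no strong reason to hypothesize a difference in efficacy based on these characteristics". The same section sets the threshold for everything outside the primary comparisons ("For non-primary comparisons, an α level of 0.05 will be used for significance") and describes the secondary and exploratory models as follows: "We will test the main effects of treatment condition", by methods similar to those for the primary endpoint.

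The primary model in Section 10.4.2 has a random participant intercept and "fixed predictors of study arm indicators, time indicators, and time by study arm interactions". Its only interaction is between time and arm.

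Section 10.2 calls the study exploratory and gives its purpose: "The sample size should be sufficient to provide us with effect size estimates for a larger randomized controlled trial". Section 5.5 stratifies randomization by SNAP/WIC receipt only, so neither sex/gender nor race/ethnicity is balanced by design.

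**The concern.** A differential effect is a difference between two treatment effects. Fitting the model separately in men and in women gives two treatment effects but not their difference, and the plan does not say how the two will be compared. With a 0.05 threshold set for all non-primary comparisons, the easiest comparison is to note which subgroup reached significance. That comparison is unreliable. Each subgroup has low power, so two subgroups with the same true effect will often fall on opposite sides of 0.05. When the subgroups are unequal in size, the larger one will usually be the one that appears to benefit.

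What is at stake is a reading such as effective in women but not in men, or the same by race/ethnicity, being carried into the larger trial that this study is meant to inform. The useful output for that purpose is an estimate of effect modification with its uncertainty, and none is planned.

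**Working it through.** **Is a comparison specified anywhere?** Sections 10.1 to 10.4.4 were read for a subgroup-by-arm term, a contrast of subgroup effects, or an interval or test for one. None appears. The plan states no figure for the subgroup analyses, so there is nothing of its own to reproduce.

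**Inputs.** From the documents: 105 participants allocated 1:1:1 (Sections 4.1 and 5.5), so 105/3 = 35 per arm; alpha 0.05 (Section 10.4.3), taken as two-sided. Assumed, because the documents give no values: the true effect d in SD units, the subgroup mix (the same in each arm) and no dropout. The setting is one active arm against BWL-Alone, compared at a single time by t-test.

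**Two subgroups with the same true effect.** Let p1 and p2 be the power in subgroups of n1 and n2 per arm (non-central t with 2n − 2 df and non-centrality d√(n/2)). The chance that exactly one is significant is p1(1 − p2) + p2(1 − p1). At d = 0.5:

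| Split per arm | p1 | p2 | Exactly one significant | Of those, larger subgroup significant |
|---|---|---|---|---|
| 18/17 | 0.308 | 0.293 | 0.421 | 52% |
| 28/7 | 0.451 | 0.139 | 0.465 | 84% |
| 30/5 | 0.478 | 0.108 | 0.483 | 88% |

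For 28/7: 0.451 × 0.861 + 0.139 × 0.549 = 0.388 + 0.076, which is 0.465 before rounding.

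Over splits 18/17, 25/10, 28/7 and 30/5:

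| d | Exactly one significant |
|---|---|
| 0 | 2 × 0.05 × 0.95 = 0.095 |
| 0.2 | 0.161–0.164 |
| 0.3 | 0.239–0.249 |
| 0.4 | 0.331–0.361 |
| 0.7 | 0.499–0.674 |

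At d = 0.5 the near-even split already gives 42%, so low power is the main cause. Imbalance adds a little to the rate and mostly determines which subgroup looks favoured.

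**Three race/ethnicity categories.** The chance of mixed significance is 1 − P(all significant) − P(none significant). Over 12/12/11, 20/10/5 and 25/6/4 per arm it is 0.1425 at d = 0, 0.207–0.209 at 0.2, 0.285–0.291 at 0.3, 0.386–0.400 at 0.4 and 0.696–0.759 at 0.7.

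**Precision of the missing estimate.** The SE of the difference between two subgroup effects is √(2/n1 + 2/n2) SD. With two arms and two subgroups, df = 70 − 4 = 66 and t = 1.997.

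| Split per arm | SE | 95% half-width | Difference for 80% power |
|---|---|---|---|
| 18/17 | 0.478 | 0.955 | 1.36 |
| 28/7 | 0.598 | 1.193 | 1.70 |
| 30/5 | 0.683 | 1.364 | 1.94 |

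For comparison, the SE of the overall contrast is √(2/35) = 0.239 SD. The difference between subgroups is therefore estimated with 2.0 to 2.9 times that standard error (0.478/0.239 to 0.683/0.239).

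**The case against.** The strongest reply has four parts.

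- The sentence stating the aim does not restrict the method and could be read as intending an interaction test. That reading is possible. But separate analyses are the only method named, so if an interaction was meant the plan needs to say so.
- The subgroups contain different participants, so anyone can subtract the two estimates and combine their standard errors. This is true, and it makes the gap smaller than a missing dataset or a wrong model. The plan still commits to neither the difference nor its standard error.
- The discordance figures depend on comparing significance across subgroups, which the plan never proposes, and on assumed effects and splits in a simple t-test setting. This stands. They illustrate a risk and do not measure a harm in this trial. One illustrated split (25/6/4) also includes a category small enough that a sensible rule would merge it.
- The analyses are labelled exploratory, sex/gender and race/ethnicity appear in no hypothesis or listed endpoint, and Section 10.2 does not mention effect modification. This limits the importance of the point. It does not make separate fits estimate the quantity that Section 10.4.3 says it wants.

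**Conclusion.** The concern holds. Section 10.4.3 names an aim and a method that does not deliver it, and no estimate, interval or test of the difference between subgroup effects is specified elsewhere in Section 10.

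If significance is compared across two subgroups with equal true effects, they will appear to differ in 16% to 25% of trials at 0.2 to 0.3 SD and in 33% to 67% at 0.4 to 0.7 SD. These rates rest on assumed effects and splits, 35 per arm, no dropout and one arm contrast. There are three arm contrasts and several endpoints, so the occasions for such a reading are more numerous than one contrast suggests.

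The importance is low: an optional improvement to an exploratory analysis, with no bearing on the primary or secondary conclusions.

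**What to change.** In Section 10.4.3, replace the separate analyses with one mixed model fitted to all randomized participants, taking one factor at a time and adding subgroup, subgroup-by-visit, arm-by-subgroup and arm-by-visit-by-subgroup terms. Then:

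- For each arm contrast, report the week-24 difference between subgroup effects with its 95% CI.
- Give the subgroup effects and their CIs from the same model as description only, and do not compare p-values between subgroups.
- State a minimum number per arm (for example 5) below which race/ethnicity categories are combined, and fix the grouping before outcomes are tabulated by arm.
- Keep the exploratory label. State that the interval will be wide and that a non-significant interaction is not evidence of equal effects.

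If the team prefers to keep the separate fits, the least that closes the gap is a sentence committing to the week-24 difference between them with its 95% CI.

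The cost is wording in one section, with the same data and the same type of model. The gain is an honest interval. It is not a powered test, since 80% power would need a difference between subgroup effects of roughly 1.4 to 1.9 SD.
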